8.3.2 Method of Detecting AEs and SAEs

Care will be taken not to introduce bias when detecting AEs and/or SAEs. Open-ended and non-leading verbal questioning of the subject is the preferred method to inquire about AE occurrences.

8.3.3 Follow-up of AEs and SAEs

After the initial AE/SAE report, the Investigator is required to proactively follow each subject at subsequent visits/contacts. All AEs/SAEs will be followed until resolution, stabilization, the event is otherwise explained, or the subject is lost to follow-up (as defined in Section [7.3](#)). Further information on follow-up procedures is given in [Appendix 4](#).

8.3.4 Regulatory Reporting Requirements for SAEs

- Prompt notification by the Investigator to the Sponsor of an SAE is essential so that legal obligations and ethical responsibilities towards the safety of subjects and the safety of a study treatment under clinical investigation are met.
- The Sponsor has a legal responsibility to notify both the local regulatory authority and other regulatory agencies about the safety of a study treatment under clinical investigation. The Sponsor will comply with country-specific regulatory requirements relating to safety reporting to the regulatory authority, Institutional Review Boards (IRB)/Independent Ethics Committees (IEC), and Investigators.

- Investigator safety reports must be prepared for suspected unexpected serious adverse reactions (SUSAR) according to local regulatory requirements and Sponsor policy and forwarded to Investigators as necessary.
- An Investigator who receives an Investigator safety report describing an SAE or other specific safety information (eg, summary or listing of SAEs) from the Sponsor will review and then file it along with the IB and will notify the IRB/IEC, if appropriate according to local requirements.

8.3.5 Pregnancy

For purposes of this study, a woman will be considered of childbearing potential unless documentation indicates she is permanently sterilized (ie, hysterectomy, bilateral salpingectomy or bilateral oophorectomy) or is naturally postmenopausal. Natural menopause is defined as the permanent cessation of menstrual periods, determined retrospectively after a woman who is at least 40 years of age has experienced 12 months of amenorrhea without any other obvious pathological or physiological cause. Female subjects who are permanently sterilized or are naturally postmenopausal will not be required to use contraceptives during the study.

The Investigator will review the contraception requirements for the study with each WOCBP who is considering being a subject.

Female participants of childbearing potential are eligible to participate if they agree to use a highly effective method of contraception consistently and correctly as described in [Appendix 6](#).

Details of all pregnancies in female subjects will be collected after the start of study treatment and until the study exit. If a pregnancy is reported, the Investigator should inform the Sponsor designee within 24 hours of learning of the pregnancy and should follow the procedures outlined in [Appendix 6](#).

The Investigator will (1) notify the subject's physician that the subject was enrolled in the study and treated with an investigational drug OP0201 or placebo, and (2) follow the progress of the pregnancy to term. The Investigator must document the outcome of the pregnancy and provide a copy of the documentation to the Sponsor.

Abnormal pregnancy outcomes (eg, spontaneous abortion, fetal death, stillbirth, congenital anomalies, ectopic pregnancy) are considered SAEs.

8.3.6 Adverse Events of Special Interest

Not applicable.

8.3.7 Medical Device Incidents (Including Malfunctions)

Instructions for documenting Medical Device Incidents are provided in [Appendix 9](#).

Medical devices are being provided for use in this study for delivering the study treatment via MDI. In order to fulfill regulatory reporting obligations worldwide, the Investigator is responsible for the detection and documentation of events meeting the definitions of incident or malfunction that occur during the study with such devices.

The definition of a Medical Device Incident can be found in [Appendix 9](#).

NOTE: Incidents fulfilling the definition of an AE/SAE will also follow the processes outlined in Section [8.3.3](#) and [Appendix 4](#) of the protocol.

8.3.7.1 Time Period for Detecting Medical Device Incidents

- Medical Device Incidents or malfunctions of the device that result in an incident will be detected, documented, and reported during all periods of the study in which the medical device is used.
- If the Investigator learns of any incident at any time after a participant has been discharged from the study, and such incident is considered reasonably related to a medical device provided for the study, the Investigator will promptly notify the Sponsor.

The method of documenting Medical Device Incidents is provided in [Appendix 9](#).

8.3.7.2 Follow-up of Medical Device Incidents

- All Medical Device Incidents involving an AE will be followed and reported in the same manner as other AEs (see [Appendix 4](#)). This applies to all subjects, including those who discontinue study treatment.
- The Investigator is responsible for ensuring that follow-up includes any supplemental investigations as indicated to elucidate the nature and/or causality of the incident.
- New or updated information will be recorded on the originally completed form with all changes signed and dated by the Investigator.

8.3.7.3 Prompt Reporting of Medical Device Incidents to Sponsor

- Medical Device Incidents will be reported to the Sponsor within 24 hours after the Investigator determines that the event meets the protocol definition of a Medical Device Incident.
- The Medical Device Incident Report Form will be sent to the Sponsor by email. If email is unavailable, then standard post should be utilized.
- The same individual will be the contact for the receipt of medical device reports and SAE.

8.3.7.4 Regulatory Reporting Requirements for Medical Device Incidents

- The Investigator will promptly report all incidents occurring with any medical device provided for use in the study in order for the Sponsor to fulfill the legal responsibility to notify appropriate regulatory authorities and other entities about certain safety information relating to medical devices being used in clinical studies.

The Investigator, or responsible person according to local requirements (eg, the head of the medical institution), will comply with the applicable local regulatory requirements relating to the reporting of incidents to the IRB/IEC.

8.4 Treatment of Overdose

It is unknown what dose of study treatment within a 24-hour time period would be considered an overdose. Both active ingredients in the study treatment are endogenous to the human respiratory system in very large quantities compared with the maximum study treatment dose of 40 mg per day of surfactant. Even if a subject were to administer an entire canister of the study treatment into the nostrils in 1 day, the total exposure to the active pharmaceutical ingredient would be 250 mg (approximately 3.6 mg/kg for a 70 kg adult), which is far less than exposures on a mg/kg basis for approved surfactant products that are usually given over 1 to 2 days (see Table 5 of the IB).

HFA-134a is not endogenous to the human respiratory system. As noted in Section 4.3.2 of the IB, misuse or intentional inhalation abuse may cause death without warning symptoms, due to cardiac effects. Other symptoms potentially related to misuse or inhalation abuse are: anesthetic effects, light-headedness, dizziness, confusion, incoordination, drowsiness, or unconsciousness, irregular heartbeat with a strange sensation in the chest, heart thumping, apprehension, feeling of fainting, dizziness or weakness. Vapors are heavier than air and can cause suffocation by reducing oxygen available for breathing. However, the maximum amount of 10 mL of HFA-134a per study treatment canister would not be sufficient exposure to be considered an overdose. If symptoms described above were experienced with a suspected HFA-134a overdose, the suggested treatment would be to deliver oxygen and other necessary supportive care per the Investigator's judgement.

In the event of an overdose, the Investigator should:

- Contact the Medical Monitor immediately.
- Closely monitor the participant for any AE/SAE and laboratory abnormalities for at least 2 days.
- Document the quantity of the excess dose as well as the duration of the overdose in the eCRF.

Decisions regarding dose interruptions or modifications will be made by the Investigator in consultation with the Medical Monitor based on the clinical evaluation of the subject.

8.5 Pharmacokinetics

Planned time points for all PK assessments are provided in the SoA (Section 1.3).

8.5.1 Collection of Samples

On Days 1 and 14, blood samples will be collected for the determination of DPPC and CP concentrations only for subjects in Cohort B. The SoA (Section 1.3) presents the schedule for blood collection. Time 0 is defined as the time of the study treatment administration.

The timing of scheduled samples may be adjusted according to clinical needs or needs for PK data. The actual collection times must be recorded. The time and date of study treatment administration will also be recorded. Instructions for the collection and handling of biological samples will be provided by the Sponsor or designee. Blood samples will be collected via a venous cannula or direct venipuncture. Samples will be collected, labeled, stored, and shipped as detailed in the Laboratory Manual. The total volume of blood taken for PK and pharmacodynamic sampling during the study will not exceed 450 mL. For specific sampling volumes, please refer to the Laboratory Manual.

The 5-minute PK sample should be collected within ± 2 minutes of the scheduled time and the 20-minute PK sample should be collected within $+5$ minutes of the scheduled time. All other PK samples should be collected within ± 5 minutes of the scheduled time.

8.5.2 Determination of Drug Concentration

Samples for the determination of DPPC and CP in serum will be analyzed on behalf of the Sponsor by [REDACTED] using appropriate validated bioanalytical methods. Full details of the bioanalytical methods will be described in a separate Bioanalytical Report.

All samples still within the known stability of DPPC and CP at the time of receipt by the bioanalytical laboratory will be analyzed.

Baseline samples collected from subjects who received placebo will be analyzed to establish the endogenous DPPC and CP concentrations. Samples collected after dosing from subjects who received placebo will not be analyzed.

Samples collected for analyses of DPPC and CP concentration may also be used to evaluate safety aspects related to concerns arising during or after the study.

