
 To evaluate the safety and tolerability of OP0201 30 mg per day (given as 2 sprays per nostril 3 times a day [TID] for 14 consecutive days) and OP0201 60 mg per day (given as 4 sprays per nostril TID for 14 consecutive days) compared to 0 mg placebo (HFA-134a only) administered in a similar parallel-group fashion TID for 14 consecutive days in healthy adult volunteers. 	
 Adverse events (AEs), otoscopy, tympanometry, nasal and epipharynx endoscopy, University of Pennsylvania Smell Inventory Test (UPSIT) olfactory test, audiology pure tone hearing test, triplicate 12-lead electrocardiogram (ECG), physical examination, vital signs, and clinical laboratory tests.

Secondary/Exploratory	

 • To evaluate if any systemic exposure of DPPC can be detected in serum at levels higher than endogenous DPPC levels in serum in up to 15 healthy adult volunteers who will be evaluated in the Cohort B dose (OP0210 60 mg per day) versus placebo. • To evaluate if any systemic exposure of CP can be detected in serum at levels higher than endogenous CP levels in serum in up to 15 healthy adult volunteers who will be evaluated in the Cohort B dose (OP0210 60 mg per day) versus placebo. 	
 • Maximum baseline adjusted serum concentration (C_{max}) of DPPC on Day 14. • Time to maximum concentration (t_{max}) of DPPC on Day 14. • Maximum baseline adjusted serum concentration (C_{max}) of CP on Day 14. • Time to maximum concentration (t_{max}) of CP on Day 14. • Additional parameters may be calculated, if appropriate.

Overall Design:

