9.3 Populations for Analyses

For purposes of analysis, the analysis sets in [Table 7](#) are defined.

Table 7 Analysis Sets

Analysis Set	Description
Entered Analysis Set	All subjects who sign the informed consent form.
Safety Analysis Set	All subjects who receive any study treatment (OP0201 or placebo). Subjects will be analyzed according to the treatment they received.
Pharmacokinetic Analysis Set	All subjects in Cohort B who received at least 1 dose of OP0201 and have 1 quantifiable serum DPPC or CP concentration collected post-dose without important protocol deviations/violations or events thought to significantly affect the pharmacokinetics.

CP = cholestryol palmitate; DPPC = dipalmitoylphosphatidylcholine

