2.2. SECONDARY OBJECTIVES

- To evaluate if any systemic exposure of dipalmitoylphosphatidylcholine (DPPC) can be detected in serum at levels higher than endogenous DPPC levels in serum in up to 15 healthy adult volunteers who will be evaluated in the Cohort B dose (OP0210 60 mg per day) versus placebo.
- To evaluate if any systemic exposure of cholestryl palmitate (CP) can be detected in serum at levels higher than endogenous CP levels in serum in up to 15 healthy adult volunteers who will be evaluated in the Cohort B dose (OP0210 60 mg per day) versus placebo (if feasible).

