4.3. CHANGES TO ANALYSIS FROM PROTOCOL

Pharmacokinetic analysis of CP will not be completed because the quantitative method for the determination of CP is not feasible. This resulted in the below changes from the protocol to the SAP:

Protocol	SAP
Secondary Objective : To evaluate if any systemic exposure of cholesteryl palmitate (CP) can be detected in serum at levels higher than endogenous CP levels in serum in up to 15 healthy adult volunteers who will be evaluated in the Cohort B dose (OP0210 60 mg per day) versus placebo.	To evaluate if any systemic exposure of cholesteryl palmitate (CP) can be detected in serum at levels higher than endogenous CP levels in serum in up to 15 healthy adult volunteers who will be evaluated in the Cohort B dose (OP0210 60 mg per day) versus placebo (if feasible).

Secondary Endpoint: Maximum baseline adjusted serum concentration (C_{max}) of CP on Day 14.	
Maximum baseline adjusted serum concentration (C_{max}) of CP on Day 14 (if feasible).
Secondary Endpoint : Time to maximum concentration (t_{max}) of CP on Day 14.	Time to maximum concentration (t_{max}) of CP on Day 14 (if feasible).

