6.3. PHARMACOKINETIC ANALYSIS SET

The pharmacokinetic analysis set will include all subjects in Cohort B who receive at least 1 dose of study drug, OP0201 or placebo, and have at least 1 quantifiable serum DPPC concentration collected post-dose without any important protocol deviations/violations or events thought to significantly affect the PK of DPPC. Subjects in this population will be used for all PK analyses and summaries.

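### The protocol bars assay of placebo post-dose DPPC samples, yet the objective compares with placebo and the SAP puts placebo in the PK set; SAP 4.3 does not log the conflict

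*Protocol*

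**What the plan says.** - **Objective.** The Protocol Synopsis asks whether serum DPPC rises above endogenous levels in volunteers "evaluated in the Cohort B dose (OP0210 60 mg per day) versus placebo". SAP 2.2 repeats this: "Cohort B dose (OP0210 60 mg per day) versus placebo".
- **Assay rule.** Protocol 8.5.2 has placebo baseline samples assayed to establish endogenous levels, then says: "Samples collected after dosing from subjects who received placebo will not be analyzed". The same section also says: "All samples still within the known stability of DPPC and CP at the time of receipt by the bioanalytical laboratory will be analyzed".
- **PK set, protocol.** Table 7 in Protocol 9.3 limits it to OP0201 recipients: "All subjects in Cohort B who received at least 1 dose of OP0201".
- **PK set, SAP.** SAP 6.3 widens it to "all subjects in Cohort B who receive at least 1 dose of study drug, OP0201 or placebo", and requires "at least 1 quantifiable serum DPPC concentration collected post-dose".
- **Reporting.** SAP 16.1 and 16.2 summarize concentrations and PK parameters by treatment.
- **Logged changes.** SAP 4.3 gives one reason for departing from the protocol: "Pharmacokinetic analysis of CP will not be completed because the quantitative method for the determination of CP is not feasible". Neither the wider PK set nor the assay rule is mentioned.

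**The concern.** The assay rule removes the data that the objective and the SAP need. A placebo subject enters the SAP PK set only with a post-dose DPPC value, and the protocol says no such value will be produced. The two documents also define the PK set differently, with no record of the change.

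If the protocol rule is followed, the only reference for Day 14 is each subject's own Day 1 baseline. That baseline is drawn in the morning, before the first dose. The Day 14 samples are drawn late in the evening, after two weeks of confinement. Any time-of-day, meal or confinement effect on endogenous DPPC would be read as exposure, or would hide it. In addition, Cmax is a maximum of values floored at zero, so it is positive even when nothing is absorbed. A placebo arm on the same schedule would carry the same drift and the same bias, and the two arms could be read against each other.

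**Working it through.** **1. Who can enter the SAP PK set.** Cohort B has 15 subjects allocated 4:1: 15 × 4/5 = 12 OP0201 and 15 × 1/5 = 3 placebo, which matches Protocol Table 5. Footnote s of the Schedule of Activities gives 2 Day 1 and 5 Day 14 samples per subject.

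- Placebo baseline samples, assayed: 3 × 2 = 6.
- Placebo Day 14 samples: 3 × 5 = 15, of which 3 × 4 = 12 follow the last dose.
- Placebo subjects who can meet SAP 6.3: 0 of 3 under Protocol 8.5.2; up to 3 of 3 if the samples are assayed. Three is the minimum in SAP 7.1 for full descriptive statistics.

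**2. Clock times.** Dosing is at 09:00, 16:00 and 23:00. Baseline (SAP 7.5) is the mean of the Day 1 samples at about 08:00 and 08:30. The Day 14 samples fall at about 22:30, 23:05, 23:20, 23:35 and 23:50, some 14 to 16 clock-hours later. The 22:30 sample follows 41 of the 42 doses (3 × 14 = 42). It is matched for time of day, but it addresses only a rise after the last dose, not accumulation.

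**3. Cmax with no absorption.** The documents give no SD, so the unit is the within-subject SD. Total within-subject variance is set to 1, with a between-day share *f* assumed at 0, 0.5 or 0.8 and normal values. Baseline is the mean of 2 Day 1 values, and Cmax = max over *k* Day 14 samples of max(0, observed − baseline). SAP 16.2 does not say whether the Day 14 predose sample counts, so *k* = 4 and *k* = 5 are both shown (400,000 simulated subjects).

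| | f = 0 | f = 0.5 | f = 0.8 |
|---|---|---|---|
| k = 4: mean Cmax | 1.102 | 0.934 | 0.796 |
| k = 4: share above zero | 0.850 | 0.723 | 0.633 |
| k = 5: mean Cmax | 1.213 | 1.000 | 0.833 |
| k = 5: share above zero | 0.885 | 0.750 | 0.652 |
| k = 4, drift +1 SD: mean | 2.034 | 1.771 | 1.554 |
| k = 5, drift +1 SD: mean | 2.163 | 1.860 | 1.603 |
| k = 4, drift −1 SD: mean | 0.411 | 0.364 | 0.308 |
| k = 5, drift −1 SD: mean | 0.472 | 0.402 | 0.327 |

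By subtraction, a +1 SD drift adds 0.76 to 0.95 SD (1.554 − 0.796; 2.163 − 1.213). A −1 SD drift removes only 0.49 to 0.74 SD (0.796 − 0.308; 1.213 − 0.472), because of the floor.

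**4. Day 14 predose as the reference.** With a floored maximum of 4, the mean is still 1.16, 0.82 and 0.52 SD for the three values of *f*. The share above zero is 4/5, since each of 5 exchangeable values is equally likely to be the largest.

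**5. Precision with placebo assayed**, in SDs of the compared variable:

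- 12 v 3: SE = √(1/12 + 1/3) = 0.645; t(13) = 2.160; half-width = 1.39.
- 12 v 2: SE = √(1/12 + 1/2) = 0.764; t(12) = 2.179; half-width = 1.66. SAP 7.1 would then give only N, n, minimum and maximum for placebo.

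The simulated SD of Cmax with no absorption is about 0.88 to 0.96, so the 12 v 3 half-width is about 1.23 to 1.34 within-subject SD.

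**6. Direction of the correction.** SAP 16.1, as worded, takes the observed level away from baseline. Programmed literally (f = 0, k = 4), a true +1 SD rise lowers mean Cmax from about 1.10 to 0.41. This is a separate error, but any reporting of Cmax depends on correcting it.

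**The case against.** The strongest reply is that the defect is mainly documentary. SAP version 2.0 is later than Amendment 1, and its PK set suggests that placebo post-dose assays were intended. The bias then arises only if the protocol rule is still followed. That is fair, but neither document records such a decision or says that the samples are assayed, so the conflict stands.

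Within Protocol 8.5.2, the specific placebo sentence can be read as an exception to the general stability sentence, and it agrees with Table 7. The objective can also be read narrowly, with placebo baselines supplying the endogenous level. Both readings are possible. Neither rescues SAP 6.3, which needs a post-dose value.

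The Day 14 sample before the last dose is labelled predose in the SAP, so whether the protocol rule covers it is arguable. If it does not, 12 further assays are needed rather than 15, and a time-matched placebo value would exist before the last dose but none after it.

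The limits of the remedy also stand. A half-width of 1.23 to 1.34 within-subject SD exceeds the no-absorption mean of Cmax in each matching scenario, so three placebo subjects cannot reliably separate bias from exposure. Much of the artefact comes from the maximum and the floor, and the observed concentrations and individual plots already planned in SAP 16.1 help with that part. The drift is hypothetical. The objective is secondary/exploratory and no hypothesis is tested.

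**Conclusion.** The concern holds. As written, the objective, the assay rule and the two PK set definitions cannot all be followed, and SAP 4.3 is silent. Under Protocol 8.5.2, 0 of 3 placebo subjects qualify for the SAP PK set and there is no placebo reference after the last dose on Day 14. A positive Cmax in the OP0201 arm alone would then not show systemic exposure. With none, mean Cmax is 0.80 to 1.10 within-subject SD for 4 samples and 0.83 to 1.21 for 5, with 63 to 89% of subjects above zero across the two.

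The conflict rests on the text alone. The sizes rest on normal values and an assumed between-day variance share of 0 to 80%; the ±1 SD drift is illustrative, and its real size and direction are unknown. This should be fixed, but it touches only the secondary/exploratory PK objective.

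**What to change.** **Preferred.**

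- Amend Protocol 8.5.2 so that the Day 14 samples of the 3 Cohort B placebo subjects are assayed. Results stay withheld until unblinding, as Protocol 8.5.3 already provides.
- Align Table 7 with SAP 6.3 and log the change in SAP 4.3.
- Report OP0201 and placebo side by side, descriptively, by time point and for Cmax, and state the n = 3 limit.
- Add the signed, unfloored change from the Day 14 predose sample at each post-dose time.
- State the correction in SAP 16.1 as observed minus baseline.

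The cost is about 15 assays, a short amendment and SAP wording, with no new subjects, visits or blood draws. SAP Appendix 2 describes PK date recording in the past tense, so samples may already be stored. If so, this depends on their being within known stability.

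**If the samples will not be assayed.** Remove the placebo comparison from the objective and placebo from the SAP PK set, correct the direction of subtraction, and describe the result as an uncontrolled change from baseline. This costs wording only.
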